	company, academic hospital, scientific organisation or investigator. A			
	party that provides funding for a study but does not commission it is not			
	regarded as the sponsor, but referred to as a subsidising party.			
Wbp	Personal Data Protection Act (in Dutch: Wet Bescherming			
	Persoonsgevens)			
WMO	Medical Research Involving Human Subjects Act (in Dutch: Wet Medisch- wetenschappelijk Onderzoek met Mensen			

SUMMARY

Rationale: Since a transfusion guideline specific for intensive care patients is currently lacking, we expect a large heterogeneity in transfusion practice worldwide.

Objective: Quantifying current transfusion practice in intensive care units(ICUs) and investigate differences in transfusion practice between and within different world regions (Europe, America and Asia).

Study design: International multicentre prospective observational point prevalence study. All patients admitted during one week will be included and followed for 28 days. Data regarding general demographic, admission data and transfusion triggers (haemoglobin level, platelet count, PT, APTT, INR, clinical indication) will be collected. For transfused patients and for non-transfused patients the nadir value of transfusion triggers will be collected. Transfusion products (red cell concentrates, plasma, platelets, fibrinogen and co-fact) will be recorded per amount and type.

Study population: Patients admitted to the ICU, 18 years or older.

Main study parameters/endpoints: The number of transfusion products per patient in relation to transfusion triggers. Differences within and between regions will be studied. Secondary outcomes are 28-day mortality and ICU length of stay in relation to transfusion strategy.

Nature and extent of the burden and risks associated with participation, benefit and group relatedness: This study is a descriptive study and only includes objective data collected as part of routine care. No intervention takes place. Therefore, this study does not result in any risk or burdens to patients.

1. INTRODUCTION AND RATIONALE

1.1 Introduction

Anaemia, thrombocytopenia and coagulopathy are common life threating issues in intensive care unit (ICU) patients and are correlated with mortality and morbidity^{1–4}. Although transfusion of blood products can be lifesaving, it might also be associated with serious adverse effects including infections and multi-organ failure^{5,6}.

During the last decades more awareness has been raised concerning the side effects of transfusion. Since the equivalence of a restrictive and liberal transfusion strategy for red blood cells was proven⁷⁻¹⁰, the transfusion practice of red blood cells has been shifted from a liberal to a more restrictive strategy^{11,12}. Guidelines are now recommending a haemoglobin threshold of <7 g/dl in most of ICU patients. Unfortunately the optimal transfusion strategy still remains debatable for several subpopulation such as patients older than 65 years and patients with acute coronary syndrome^{13,14}. Furthermore, guidelines specific for ICU patients are lacking. This discussion regarding the optimal transfusion strategy does not only apply to red blood cell products, but also concerns platelets, plasma and other coagulation factors. Where multiple large randomized trials have been performed regarding red blood cell transfusion, evidence for the optimal transfusion strategy for platelets and plasma is more limited, especially in the intensive care setting. As a result heterogeneous transfusion practice exists for these products as is shown in a study performed in the UK 2011¹⁵. This study showed an inconsistent transfusion practice regarding indications and number of transfused units of plasma. In addition, the benefit of a large amount of the transfused plasma units has never been proven¹⁵. Another study performed in Australia showed similar results, about 27-51% of all plasma transfusion were given without a proper indication¹⁶. The same holds true for platelet transfusion, 29-51% of all platelet transfusions in South-Wales Australia were transfused without a reasonable indication¹⁷. Due to the complexity and heterogeneity of the ICU patient population, current guidelines such as the NICE are not always applicable to critically ill patients¹⁸. At current, an ESICM taskforce is preparing specific blood component transfusion guidelines for the intensive care setting. It will be useful to determine current transfusion practice which can be compared in a few years after implementing this new guideline. This study aims to give an overview in current transfusion practice on the ICU worldwide. This information might help improve future guidelines, patient care and set new goals for research.

1.2 Relevance

Transfusion practice has already been studied before on the ICU and the operating theater^{17,19–21}. However, these studies were held in a limited number of hospitals within the same country, were limited to only one type of transfusion, are often outdated and difficult generalizable to other hospitals and regions. Since these large observational studies, numerous of randomized controlled trials on RBC transfusion have been published supporting the safety of more restrictive transfusion strategy^{7–10}. However, current

InPUT-study Protocol, dated 09-09-2020

transfusion practice remains unknown. There is a need 1) to describe current transfusion practice for RBC but also for other blood components and coagulation factors, 2) to identify area of improvement, 3) to have large observational data to generate hypotheses on optimal transfusion triggers in subgroups of critically ill patients including patients with brain injury, cardiovascular diseases and elderly patients.

This study will be the first worldwide transfusion practice point prevalence trial on the ICU, which studies the practice of administration of different blood products and coagulation factors.

OBJECTIVES

Primary Objective:

- Number of red blood cell, platelet, and coagulation factors in correlation to haemoglobin levels, platelet count and INR (or PT) respectively.

Secondary Objectives:

- To evaluate which other triggers such as hemodynamic or comorbidities influence RBC transfusion practice.
- To compare haemoglobin levels in transfused patients with nadir levels of haemoglobin in non-transfused patients
- To compare platelet count in transfused patients with platelet to nadir platelet count in non-transfused patients
- To compare INR (or PT) in transfused patients with plasma to nadir level of INR(PT) in non-transfused patients
- To compare transfusion practice between different subgroups of patients including shock septic, haematology, cardiovascular disease without acute coronary diseases and coronary disease
- Association between restrictive and liberal RBC transfusion strategy on ICU length of stay and 28-day mortality
- Association between restrictive and liberal platelet transfusion strategy on ICU length of stay and 28-day mortality
- Association between restrictive and liberal coagulation factor suppletion strategy on ICU length of stay and 28-day mortality

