2. STUDY DESIGN

This study is a prospective, descriptive study and only includes objective data collected as part of routine care. No intervention takes place. ICUs in different world regions will be asked to participate in this study. Each centre can choose a week to participate from several pre-specified weeks. All newly admitted patients on the ICU in that specific week will be included and followed until discharge and/or 28 days (see Figure 1 for study flow).

A transfusion event is defined as the administration of a blood derived product or coagulation factor with as aim to treat or prevent anaemia, bleeding and/or coagulopathy. This includes administration of red cell concentrates, platelet concentrates, plasma and coagulation factors including fibrinogen concentrate, cryoprecipitate and prothrombin complex. For each transfusion event data will be collected prospectively using a questionnaire on prescription behaviour. Also transfusions administered on the operating theatre while admitted to the ICU will be included for analysis.

The daily questionnaire contains clinical an laboratory data. These data include nadir haemoglobin levels, platelet count and INR or PT. This data will be necessary to compare data between patients who did receive a transfusion to patients who did not receive transfusions. Furthermore, information about 24h fluid balance and anticoagulants administration will be collected. Finally after 28 days patient outcome data: length of ICU stay and 28-day mortality will be collected.

STUDY POPULATION

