3.2 Data collection

All newly admitted patients at the ICU older than 18 years will be included for seven consecutive days. At the start, baseline characteristics will be scored prospectively. Also, patients will be scored daily using daily questionnaires until discharge with a maximum of 28 days. At the day 28, patient outcomes are scored irrespective whether they were discharged. Furthermore, for each transfusion event or administration of coagulations factors a questionnaire will be filled in. See Figure 1 for the workflow.

Figure 1. Workflow InPUT study

The following data will be collected:

Baseline characteristics:

- Demographics
- SOFA score at inclusion
- Type of admission
- Presence or absence and the type of shock on the study day
- Heart rate, systolic and diastolic blood pressure
- Ventilator settings
- Renal replacement therapy during that day

Questionnaire per transfusion event:

- General
 - \circ Active bleeding
 - Bleeding control
 - Red cell transfusion
 - Haemoglobin(Hb)/haematocrit (Ht) level
 - Hb threshold for this patient
 - Presence of physiological trigger, and which trigger has been used.
 - Transfusion relevant comorbidity

- Number of units transfused
- Origin of transfusion product (e.g. allogeneic, autologous, cell salvaged blood)
- Platelet transfusion
 - Platelet count prior to transfusion
 - Platelet count threshold for transfusion for this patient
 - Type of Platelet concentrate
 - Anticoagulant usage the past 72 hours
 - Usage of point of care to assess blood coagulation: ROTEM or multiplate
 - Number of units transfused
 - Upcoming procedures
- Plasma
 - INR prior to transfusion
 - $_{\odot}$ Anticoagulant usage the past 72 hours
 - Usage of point of care to assess blood coagulation
 - Amount of plasma transfused
 - Upcoming procedures
- Prothrombin complex concentrate (i.e. Cofact ®).
 - o INR or PT
 - Dosage of prothrombin complex concentrate
 - Usage of point of care to assess blood coagulation
 - Upcoming procedures
- Massive transfusion protocol:
 - Lowest haemoglobin level
 - Lowest platelet count
 - o INR
 - Usage of point of care to assess blood coagulation
 - Number of Red blood cell units transfused
 - Number of platelet concentrate units transfused
 - Amount of plasma transfused
 - Tranexamic acid, fibrinogen, rFactor VIIa, Cryoprecipitate, factor XIII, apropitin, novoseven (=eptacog alfa)
 - Bleeding control

Daily questionnaire

- Estimated blood loss
- Total number of transfused RBCs

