- Total number of transfused platelet concentrates
- Total ml transfused plasma
- Volume administration in 24 hours
- Lowest haemoglobin level, lowest platelet count, highest INR in 24 hours
- Tranexamic acid administration in 24 hours
- Transfusion within 24 hours outside the ICU (e.g. on operating theatre)

At day 28

- 28-day mortality
- Length of stay on ICU
- Iron administration within ICU admission

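### The INR objective names the lowest value while the daily form collects the highest, and none of the three transfused versus non-transfused comparisons fixes a common value or time window

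*Protocol*

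**What the plan says.** Three secondary objectives compare a laboratory marker between transfused and non-transfused patients:

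- Haemoglobin: "To compare haemoglobin levels in transfused patients with nadir levels of haemoglobin in non-transfused patients".
- Platelets: "To compare platelet count in transfused patients with platelet to nadir platelet count in non-transfused patients".
- INR or PT: "To compare INR (or PT) in transfused patients with plasma to nadir level of INR(PT) in non-transfused patients".

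Section 2 (Study design) describes the daily questionnaire in similar terms, "These data include nadir haemoglobin levels, platelet count and INR or PT", and gives its purpose: "This data will be necessary to compare data between patients who did receive a transfusion to patients who did not receive transfusions". The Summary, which lists PT, APTT and INR among the transfusion triggers, says: "For transfused patients and for non-transfused patients the nadir value of transfusion triggers will be collected".

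The list of daily items in section 3.2 differs for INR: "Lowest haemoglobin level, lowest platelet count, highest INR in 24 hours". These items are recorded each day until discharge, for at most 28 days. Section 3.2 also has a form per transfusion event. For plasma it holds "INR prior to transfusion", and for red cells and platelets it holds the marker level and the threshold used for that patient.

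**The concern.** There are two faults.

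First, coagulopathy shows as a raised INR. The lowest INR of a non-transfused patient is that patient's most normal value. Set against the INR of plasma recipients, it widens the contrast whatever clinicians do. It is also not what the daily form records.

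Second, the two groups are not clearly measured in the same way. The objectives specify an extreme for non-transfused patients and nothing for transfused patients. The event form supplies a natural single value for the latter. An extreme over several days moves further out as days accumulate, and patients stay for different lengths of time.

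At stake are the listed comparisons of laboratory values between transfused and non-transfused patients. They carry most weight for plasma, because the plasma event form lists no INR threshold for the patient, whereas the red cell and platelet forms each list a threshold.

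**Working it through.** No figure in the protocol bears on this point, so there is none to reproduce. The check compares the passages and adds an illustration on assumed inputs.

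**Step 1: which INR extreme.**

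| Place | Extreme for INR |
|---|---|
| Summary, study design | nadir (of the listed triggers, INR included) |
| Secondary Objectives | nadir |
| Section 2 | nadir, if the word governs the whole list |
| Section 3.2, daily questionnaire | highest in 24 hours |

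The objective cannot be met literally from the daily form, which holds no lowest INR. The smallest of the daily highest values could be computed, but that is not the nadir. The daily list also names INR only, although the objective and section 2 allow PT instead.

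**Step 2: which value in transfused patients.** The Secondary Objectives give no time point. The event form in section 3.2 and the main endpoint in section 3.1.1 use values before transfusion. The Summary can be read as nadir in both groups. The protocol does not choose between these.

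**Step 3: what an unequal window does (illustration).** Assume the same daily marker process in both groups, so that practice does not differ. Let the marker be normal with single-day SD 1 and equal within-patient correlation ρ between days. The expected minimum of k daily values then lies √(1 − ρ) × m(k) below the mean, where m(k) is the expected maximum of k independent standard normal values: m(3) = 0.846, m(7) = 1.352, m(28) = 2.014. A single-day value has expected shift 0. The correlations and day counts are assumed; 28 is the protocol's maximum.

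| Days k | ρ = 0 | ρ = 0.5 (× 0.707) | ρ = 0.8 (× 0.447) |
|---|---|---|---|
| 3 | 0.85 SD | 0.60 SD | 0.38 SD |
| 7 | 1.35 SD | 0.96 SD | 0.60 SD |
| 28 | 2.01 SD | 1.42 SD | 0.90 SD |

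The gap depends only on k and ρ. Correlation shrinks it but does not remove it.

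**Step 4: direction.** For haemoglobin and platelets, the stay minimum pulls non-transfused patients down towards the low values of transfused patients, so the artefact shrinks the contrast. For INR as worded, the minimum pulls them away from the high values of plasma recipients, so it widens the contrast.

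**Step 5: the same on an INR scale (illustration).** Assume lognormal INR with median 1.30 and log-SD 0.25, 7 daily values, ρ from 0.5 to 0.8, and no group difference. Simulated medians are:

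- single day: 1.30
- lowest of the stay: 1.03 to 1.12, so transfused patients look 0.18 to 0.27 higher (1.30 − 1.12 and 1.30 − 1.03)
- highest of the stay: 1.51 to 1.65, so they look 0.21 to 0.35 lower (1.51 − 1.30 and 1.65 − 1.30)

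Changing the word therefore cures the wrong direction but not the unequal window.

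**Step 6: would it show in a test?** Section 5.2 tests secondary parameters at p < 0.05. Section 2.4 plans 10 000 patients, with 10 to 20% receiving at least one product. With 1000 against 9000 patients and unit SD in each group, the standard error is √(1/1000 + 1/9000) = 0.033 SD, and the smallest entry above, 0.38 SD, is 0.38/0.033 ≈ 11 standard errors. With only 100 recipients of one product (assumed), it is √(1/100 + 1/9000) = 0.101 SD, and 0.38/0.101 ≈ 3.8. Clustering by ICU is ignored and would lower these ratios.

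**The case against.** The strongest defence is that the data are sound and only a word is wrong. Section 3.2 collects the clinically worse extreme of every marker, so nadir for INR reads most naturally as worst value, and in section 2 the word may govern haemoglobin alone. An analyst working from the form would not find a lowest INR. This stands in part: no data are lost, and a full lowest-to-highest INR error cannot arise from the recorded daily extremes. It does not remove the conflict, because the objective still names the wrong extreme.

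A second defence is that the summary value and window are commonly left to a statistical analysis plan, which is not at hand, and that the Summary supports nadir against nadir. This also stands in part: neither the pre-transfusion value nor a stay-long minimum is stated in the objectives. But the protocol's own wording treats the groups differently. Nadir in both would not settle it either, since a transfused patient's nadir may fall after the transfusion.

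A reader might go further and infer three things that the documents do not support:

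- *The study fails to measure transfusion triggers.* The objectives do not claim that these comparisons do so. Pre-transfusion values, patient thresholds for red cells and platelets, and physiological triggers for red cells are recorded per event, and the main endpoint uses values before transfusion.
- *The nadir is wrong for haemoglobin and platelets.* It is the right extreme and usefully describes what level was tolerated without transfusion.
- *A group difference is guaranteed because non-transfused patients are selected on their values.* They are not defined by a laboratory value. Bleeding, procedures and comorbidity are also recorded as relevant, so overlap is expected and informative. For haemoglobin and platelets the nadir works against a difference.

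**Conclusion.** The concern holds in two limited parts. The INR wording is an internal contradiction that names the least abnormal extreme; this rests on the text alone. The unequal window is the natural reading of all three objectives, but it depends on the event-form value being used for transfused patients and on the extreme being taken over more than one day.

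The size cannot be derived from the documents, because they give no within-patient variance, correlation or distribution of stay. The figures of 0.38 to 0.96 SD over 3 to 7 days, and of roughly 0.2 to 0.35 INR either way over 7 days, are illustrations on assumed inputs. The dependence on days observed does not rest on those particular values.

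The primary endpoint is untouched and the daily form already holds the right INR extreme. The point should be fixed before analysis, but it does not threaten the study's main result.

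**What to change.** 1. In the Summary, the Secondary Objectives and section 2, replace nadir by highest for INR, to match the daily questionnaire in section 3.2. State which extreme applies to PT according to how it is expressed, and whether the daily form takes PT where INR is not reported.
2. State which value and which window are compared, the same for both groups. One workable form is a patient-day analysis. For each ICU day up to the first transfusion of a product, relate transfusion of that product on that day (yes or no) to that day's lowest haemoglobin, lowest platelet count or highest INR. On transfusion days, use only values before the transfusion. Allow for clustering by ICU and patient, and report the proportion transfused by band of the marker. Other like-for-like definitions would also serve.
3. Reconcile section 3.7, which says that additional questions for non-transfused patients were dropped after the pilot, with section 2, which calls the daily data necessary for this comparison.

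Cost: a few words in three places and one modest extra analysis. The INR extreme needs no new data. If a single pre-transfusion value is used on transfusion days and a 24-hour extreme on the others, a small asymmetry within the day remains and should be acknowledged.

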2. STUDY DESIGN

This study is a prospective, descriptive study and only includes objective data collected as part of routine care. No intervention takes place. ICUs in different world regions will be asked to participate in this study. Each centre can choose a week to participate from several pre-specified weeks. All newly admitted patients on the ICU in that specific week will be included and followed until discharge and/or 28 days (see Figure 1 for study flow).

A transfusion event is defined as the administration of a blood derived product or coagulation factor with as aim to treat or prevent anaemia, bleeding and/or coagulopathy. This includes administration of red cell concentrates, platelet concentrates, plasma and coagulation factors including fibrinogen concentrate, cryoprecipitate and prothrombin complex. For each transfusion event data will be collected prospectively using a questionnaire on prescription behaviour. Also transfusions administered on the operating theatre while admitted to the ICU will be included for analysis.

The daily questionnaire contains clinical an laboratory data. These data include nadir haemoglobin levels, platelet count and INR or PT. This data will be necessary to compare data between patients who did receive a transfusion to patients who did not receive transfusions. Furthermore, information about 24h fluid balance and anticoagulants administration will be collected. Finally after 28 days patient outcome data: length of ICU stay and 28-day mortality will be collected.

STUDY POPULATION

2.1 Population

All newly admitted patients on the ICU in a pre-specified week (7 days).

2.2 Inclusion criteria

All patients admitted to the ICU in a pre-specified week.

2.3 Exclusion criteria

Patients younger than 18 years old.

2.4 Sample size calculation

It is planned to recruit 10 000 patients. The CRIT study and European data reported RBC transfusion rate of 30 to 40% for patients during their stay on the ICU. Furthermore transfusion rates for platelet concentrates and plasma of 12% and 9% have been reported^{17,22}. However, in this study we will include all transfusion events during a prespecified week and day. Depending on the study design, it is estimated that approximately 10-20% of all patients will receive at least one blood product, resulting in a total of approximately 1000-2000 transfusion events. As for the primary outcome merely descriptive statistics will be used, this will be a sufficient number of transfusion events. This is in accordance with data available from the most recent study investigating transfusion practices worldwide, in which 10.069 patients were included¹⁹.

